Multc Lean Desktop (version 2.1.0) was used to generate the toxicity and futility stopping boundaries and the operating characteristics table. In order to utilize the software for the design, a 59% constant rate, a 6% delta and beta (1.18, 0.82) priors were assumed for the standard treatment response rate and experimental treatment response prior distribution, respectively. In addition, a 30% constant rate and beta (0.6, 1.4) priors were assumed for the standard treatment toxicity rate and experimental treatment toxicity prior distribution, respectively.

Cohort B:

The target CR/CRi/MLFS rate is 35% evaluated within 6 cycles of treatment. A >30% clinically significant drug-related grade 3 or higher toxicity rate occurred in the 1st cycle is considered unacceptable. A sample size of 20 patients ensures that, if the cohort is not terminated early, a posterior 95% credible interval for CR/CRi/MLFS will be (0.17, 0.56) under the assumption of a 35% of CR/CRi/MLFS and prior Beta (0.7, 1.3). Thus, interim monitoring rules, assuming the prior distributions below, were constructed that meet the following two conditions,

- 1) Stop if Prob[p(CR/CRi, E) < 0.35 | data] > 0.95, or
- 2) Stop if Prob[p(TOX, E) > 0.30 | data] >0.93,

where p(CR/CRi/MLFS, E) and p(TOX, E) are the true CR/CRi/MLFS and toxicity rates for the regimen. The first rule provides for stopping the study if the data suggest that it is unlikely (i.e., probability < 5%) that CR/CRi/MLFS rate of the regimen is greater than 35%. The second condition will stop the study early if excessive therapy-related grade 3 or higher toxicity (>30%) is highly probable (i.e., probability >93%) for the combination treatment. Monitoring for toxicity and futility will not begin until 4 patients have been evaluated, and cohort size for future evaluations is 4.

The monitoring rule for the toxicity and CR/CRi/MLFS rates, based on these assumptions and monitoring conditions above is found in Table 3. For example, accrual will cease if 3 or more patients experience toxicities among the first 4 patients. Accrual will cease if no patient experience an overall response in the first 8 patients treated.

Table 3. stopping boundary for efficacy and toxicity				
# patients avaluated	Stop the cohort if there are	this number of patients		
# patients evaluated	<pre># patients with CR/CRi/MLFS</pre>	# patients with toxicities		
4	Never stop	3-4		
8	0	5-8		

12	0-1	7-12
16	0-2	8-16

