20	Stop due to maximum sample size	Stop due to maximum sample size

Table 4 shows the operating characteristics for simultaneous monitoring response and toxicity rates. The probability of stopping the study early if the true CR/CRi/MLFS of the combination treatment was 35% and the true toxicity rate was 30% was 21%. Probabilities of stopping early for high true toxicity rates (i.e., 50%) were 75% when the true CR/CRi/MLFS was 35%.

Table 4. Operating characteris	tics for simultaneous monitoring	response and toxicity rates
True Toxicity Rate	True CR/CRi/MLFS	Prob(stop the cohort early)
0.20	0.25	0.2785
	0.30	0.1728
	0.35	0.1076
	0.40	0.0709
	0.45	0.0519
0.30	0.25	0.3628
	0.30	0.2694
	0.35	0.2118
	0.40	0.1794
	0.45	0.1626
0.40	0.25	0.5372
	0.30	0.4695
	0.35	0.4276
	0.40	0.4041
	0.45	0.3919
0.50	0.25	0.7544
	0.30	0.7184
	0.35	0.6962
	0.40	0.6837
	0.45	0.6772

Multc Lean Desktop (version 2.1.0) was used to generate the toxicity and futility stopping boundaries and the operating characteristics table. In order to utilize the software for the design, a 35% constant rate and beta (0.7, 1.3) priors were assumed for the standard treatment response rate and experimental treatment response prior distribution, respectively. In addition, a 30% constant rate and beta (0.6, 1.4) priors were assumed for the standard treatmental treatment toxicity prior distribution, respectively.

Analysis Plan: Demographic/clinical characteristics and safety data of the patients will be summarized using descriptive statistics such as mean, standard deviation, median and range.

For the primary efficacy analysis, we will estimate the CR/CRi/MLFS for the combination treatment (defined as the proportion of patients achieving CR or CRi or MLFS within 6 cycles of treatment), along with the 95% credible interval. This regimen will be considered worthy of further investigation if a CR/CRi/MLFS rate of at least 35% is achieved for frontline patients (Cohort B). Other efficacy endpoints (e.g. CR rate, CR/CRi rate, minimal residual disease negativity, or proportion of patients proceeding to HSCT) will also be estimated along with 95% credible intervals. The association between response and patient's clinical characteristics (e.g., baseline apoptotic protein levels, baseline FLT3 allelic ratio, or baseline genomic alterations) will be examined by Wilcoxon's rank sum test or Fisher's exact test, as appropriate.

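### Cohort B's final go rule has no toxicity condition, so it can be positive when the plan's own toxicity criterion is met on all 20 patients

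*Combined protocol and SAP*

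**What the plan says.** All of this is in section 10 (Statistical Methodology) unless noted.

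- **Unacceptable toxicity.** The Cohort B text says: "A >30% clinically significant drug-related grade 3 or higher toxicity rate occurred in the 1st cycle is considered unacceptable".
- **Interim toxicity rule, Cohort B.** "Stop if Prob[p(TOX, E) > 0.30 | data] >0.93". Looks follow this schedule: "Monitoring for toxicity and futility will not begin until 4 patients have been evaluated, and cohort size for future evaluations is 4". Table 3 gives toxicity limits at 4, 8, 12 and 16 patients. Its row for 20 reads only "Stop due to maximum sample size".
- **Final verdict.** The Analysis Plan says: "This regimen will be considered worthy of further investigation if a CR/CRi/MLFS rate of at least 35% is achieved". The sentence goes on to call Cohort B frontline patients. Elsewhere Cohort B is the relapsed/refractory cohort, and the response endpoint and the 35% target belong to it, so I read the sentence as the Cohort B rule.
- **Final safety analysis.** Safety data are summarised descriptively, with no decision attached.
- **Other safeguards.** There is a lead-in of six Cohort B patients, in which two or more DLTs defer accrual. Section 7.2 provides for continuous toxicity monitoring and section 12 for DSMC oversight. None of these is a condition of the final verdict.

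**The concern.** The plan sets a toxicity level it regards as unacceptable and a posterior criterion for recognising it, but uses that criterion only to halt accrual. Once 16 patients have passed, cycle-1 toxicity in the last four enters no rule, and the verdict is read from response alone. The stated rule can then call a regimen worthy of further study on the same 20 patients for whom the plan's own criterion says that toxicity is too high. A reader of the final report would have no prespecified way to resolve that conflict.

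**Working it through.** **Inputs (section 10, Cohort B).** Toxicity prior: "a 30% constant rate and beta (0.6, 1.4) priors were assumed". Response prior: "a 35% constant rate and beta (0.7, 1.3) priors were assumed". Futility rule: "Stop if Prob[p(CR/CRi, E) < 0.35 | data] > 0.95", read as CR/CRi/MLFS, as the text after it does. Cutoffs are 0.93 (toxicity) and 0.95 (futility), with looks at 4, 8, 12 and 16 and a maximum of 20.

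**Step 1: reproduce the plan.** With k toxicities in n patients the posterior is Beta(0.6 + k, 1.4 + n − k). P(toxicity > 0.30) first exceeds 0.93 at:

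- 3/4: 0.935 (2/4: 0.734)
- 5/8: 0.954 (4/8: 0.846)
- 7/12: 0.969 (6/12: 0.905)
- 8/16: 0.940 (7/16: 0.855)

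These are the Table 3 limits. Exact enumeration of (responses, toxicities) over the four looks, with the two outcomes independent, gives early-stopping probabilities at 35% response of 0.1076, 0.2118, 0.4276 and 0.6962 for true toxicity of 20%, 30%, 40% and 50%. These equal the Table 4 entries. (The prose above Table 4 gives 75% for the last setting. The table entry is 0.6962, and 0.7544 is the entry for 25% response. That is a separate slip and does not affect this point.) The credible interval at 7/20 responses is (0.170, 0.556), matching the stated (0.17, 0.56).

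**Step 2: what counts as a positive verdict.** 35% of 20 is 7 responses. Reading the rule as a posterior mean gives the same threshold: (0.7 + 7)/22 = 0.350, against (0.7 + 6)/22 = 0.305 for six.

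**Step 3: the toxicity criterion at 20 patients.** The posterior is Beta(0.6 + k, 21.4 − k).

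- 9/20: 0.906
- 10/20: 0.961
- 11/20: 0.986

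The 0.93 cutoff is therefore crossed from 10/20. A cohort at 7/16 continues (0.855). Three of the last four then give 10/20, and four of four give 11/20, the highest count reachable. With at least 7 responses either result is a positive verdict.

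**Step 4: how often.** Same enumeration, lead-in not applied. The last column adds the condition of fewer than 10/20 toxicities; last digits may differ by rounding.

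| True toxicity | True response | Reach 20 | Positive verdict | Positive with ≥10/20 toxicities | Positive after fix |
|---|---|---|---|---|---|
| 20% | 35% | 0.8924 | 0.5590 | 0.0003 | 0.5588 |
| 20% | 45% | 0.9481 | 0.8360 | 0.0004 | 0.8356 |
| 30% | 35% | 0.7882 | 0.4937 | 0.0042 | 0.4896 |
| 30% | 45% | 0.8374 | 0.7384 | 0.0062 | 0.7322 |
| 40% | 35% | 0.5724 | 0.3586 | 0.0165 | 0.3421 |
| 40% | 45% | 0.6081 | 0.5362 | 0.0247 | 0.5116 |
| 50% | 35% | 0.3038 | 0.1903 | 0.0263 | 0.1640 |
| 50% | 45% | 0.3228 | 0.2846 | 0.0393 | 0.2453 |

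**Step 5: the lead-in.** The DLT definition in section 4.9 has its own exceptions and windows, so it is not the monitored toxicity. As one end of a range, assume that the two are identical and that two or more of the first six ends the path. At 35% to 45% response the contradiction then falls to 0.0030–0.0045 at 40% toxicity and 0.0048–0.0071 at 50%. The probability of a positive verdict falls to 0.129–0.193 and 0.054–0.080. The other end of the range is the table above.

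**The case against.** **The rule is an efficacy statement.** It sits in the primary efficacy paragraph. Safety is a secondary objective, reported alongside, and nobody would take a 20-patient single-arm result forward without looking at toxicity. That is fair, and the omission invalidates no estimate or boundary. But the sentence is the only criterion the plan gives for going on, and it is worded as a verdict on the regimen.

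**The lead-in, continuous monitoring and the DSMC protect patients.** They do. A reader might infer that toxicity goes unchecked, and the documents do not support that. The gap is only in what the final verdict depends on.

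**The row for 20 patients is not an error.** A reader might call the missing limit there a defect of Table 3. It is not: the table governs accrual, and at 20 there is none left to stop. The remedy belongs in the final decision rule.

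**Reaching 20 is not endorsement.** A reader might take every cohort that reaches 20 at 50% true toxicity (30% to 32%, from Table 4 at 35% to 45% response) as a verdict given regardless of toxicity. Cohorts with fewer than 7 responses get no positive verdict; the figure is 0.19 to 0.28.

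**Cohort A.** A reader might extend the point there. Cohort A's primary endpoint is one-year survival and it has no such go rule, so there is no verdict to contradict.

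**Conclusion.** The point holds for Cohort B as an inconsistency between the final rule and the plan's own toxicity criterion. The direct contradiction (at least 7 responses with at least 10/20 toxicities) has probability 0.0165–0.0247 at 40% true toxicity and 0.0263–0.0393 at 50%, for true response of 35% to 45%. It falls below 1% if lead-in DLTs are assumed to coincide with the monitored toxicity.

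The broader consequence is larger. Before the lead-in, a regimen with 40% true toxicity is called worthy with probability 0.36–0.54, and one with 50% with probability 0.19–0.28. Most of that comes from the verdict's silence on toxicity together with the high certainty (0.93) needed to stop, not from the absence of a limit at 20.

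The figures assume that response and toxicity are independent, as the reproduced Table 4 does, and that all 20 patients are evaluable for both. It is an inexpensive improvement to the decision rule, not a flaw in the monitoring design.

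**What to change.** In the Analysis Plan, make the Cohort B verdict depend on two conditions: a CR/CRi/MLFS rate of at least 35%, and the existing toxicity criterion (posterior P(toxicity > 0.30) above 0.93) not met on all 20 patients. With 20 evaluable patients, 10 or more toxicities would fail. Stating the posterior form as well covers a different denominator. Report the final posterior P(toxicity > 0.30) and the credible interval for the toxicity rate in both cohorts. Correct the frontline label in the same sentence.

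**Cost.** One clause, with no extra patients or data. Positive verdicts fall by 0.03 to 0.04 percentage points at 20% true toxicity and by 0.4 to 0.6 points at 30%.

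**Limit of the fix.** It only aligns the verdict with the plan's own cutoff. At 35% response the probability of a positive verdict falls from 0.359 to 0.342 at 40% toxicity and from 0.190 to 0.164 at 50%, and 9/20 (45%) would still pass. Whether to use a stricter final criterion is the sponsor's choice. To show the trade-off only: also requiring observed toxicity of at most 6/20 would give 0.138 and 0.032 in those two settings, while at 20% toxicity positive verdicts would fall from 0.559 to 0.520 (35% response) or from 0.836 to 0.777 (45% response).

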2. STUDY OBJECTIVES AND ENDPOINTS

2.1. Primary Objectives

- Cohort A: To determine overall survival rate at 1 year of the regimen in patients with newly diagnosed AML
- Cohort B: To determine the complete remission(CR)/Complete remission without recovery of counts (CRi)/morphologic leukemia-free state (MLFS) rate of the regimen in patients with relapsed/refractory AML or high-risk MDS

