2.2 Secondary Objectives

- To assess other efficacy endpoints (CR rate, minimal residual disease negativity by flow cytometry, relapse-free survival, event-free survival, and overall survival)
- To assess proportion of patients proceeding to HSCT
- To determine the safety of the combination regimen

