3.1 Inclusion Criteria

- 1. Diagnosis:
 - a) Cohort A (frontline): Adults ≥18 years with newly diagnosed AML.
 - b) Cohort B (relapsed/refractory): Adults ≥18 years with relapsed/refractory AML or relapsed/refractory MDS or CMML that is intermediate-2 or high-risk by the International Prognostic Scoring System with ≥10% blasts harboring a Ras pathway-activating mutation. Eligible mutations include: activating mutations of KIT, HRAS/NRAS/KRAS, BRAF, CBL or PTPN11 or loss of function mutation of NF1. Other mutations not listed here that are anticipated to activate Ras signaling may be considered for enrollment after discussion with the PI.
- 2. Performance status \leq 2 (ECOG Scale).
- 3. Adequate liver and renal function as defined by the following criteria:
 - a) Total serum bilirubin < 2.5 x upper limit of normal (ULN), unless due to Gilbert's syndrome, hemolysis or the underlying leukemia approved by the PI
 - b) Alanine aminotransferase (ALT) or aspartate aminotransferase (AST) \leq 3 x ULN, unless due to the underlying leukemia approved by the PI
 - d) Creatinine clearance ≥30 mL/min
- 4. Ability to swallow
- 5. Signed informed consent

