10. STATISTICAL METHODOLOGY

This is an open label, phase II study with a lead-in phase to assess the MTD and the efficacy of the combination regimen of azacitidine, venetoclax, and trametinib in patients with AML or MDS/CMML. A total of 40 patients will be enrolled for the study: 20 patients with newly diagnosed AML (Cohort A) and 20 patients with relapsed/refractory AML or higher-risk MDS or CMML (Cohort B).

In order to confirm the safety of azacitidine, venetoclax, and trametinib, there will be a lead-in phase for the regimen safety. The regimen will initially be explored in 6 eligible patients meeting criteria for enrollment in Cohort B (i.e. relapsed/refractory). If none or only one of the 6 patients experiences DLT in first cycle attributable to the treatment components, the phase II portion of the study will proceed as detailed below. The patients treated in this confirmatory phase will be counted towards the phase II component of the study. If DLT attributable to the components is observed in 2 or more of these initial 6 patients, accrual to the phase II portion of the study will be deferred, and a lower dose of the combined agents would be assessed based on the investigators' decision, which will be implemented with amendment to the study.

Cohort A:

The historical 1-year overall survival rate (OSR) for newly diagnosed patients is 59% and for this cohort the target OSR is 65% for the experimental treatment. A >30% clinically significant drug-related grade 3 or higher toxicity rate occurred in the 1st cycle is considered unacceptable. A sample size of 20 patients ensures that, if the cohort is not terminated early, a posterior 95% credible interval for OSR will be (0.38, 0.78) under the assumption of a 59% of OSR and prior Beta (1.18, 0.82). Thus, interim monitoring rules, assuming the prior distributions below, were constructed that meet the following two conditions,

- 1) Stop if Prob[p(OSR, H) + δ_{OSR} > P(OSR, E) | data] > 0.95, where δ_{OSR} = 0.06 or
- 2) Stop if Prob[p(TOX,H) + δ_{TOX} < p(TOX,E)| data] > 0.90, where δ_{TOX} = 0,

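### The Analysis Plan contradicts the primary objectives: it makes CR/CRi/MLFS the primary efficacy analysis without limiting it to Cohort B, leaves out Cohort A's 1-year survival, and calls Cohort B frontline in its only success rule

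*Combined protocol and SAP*

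**What the plan says.** Section 2.1 sets two primary objectives. One reads "Cohort A: To determine overall survival rate at 1 year of the regimen in patients with newly diagnosed AML". The other, for Cohort B, is the CR/CRi/MLFS rate in relapsed/refractory AML or high-risk MDS. Section 3.1 labels Cohort A as frontline and defines the other group as "Cohort B (relapsed/refractory): Adults ≥18 years with relapsed/refractory AML", continuing with relapsed/refractory MDS or CMML. Section 4.5 puts 20 patients in each cohort.

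The design part of Section 10 follows this split. For Cohort A: "The historical 1-year overall survival rate (OSR) for newly diagnosed patients is 59% and for this cohort the target OSR is 65" per cent. For Cohort B: "The target CR/CRi/MLFS rate is 35% evaluated within 6 cycles of treatment".

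The Analysis Plan at the end of Section 10 does not follow it. It opens with "For the primary efficacy analysis, we will estimate the CR/CRi/MLFS for the combination treatment", names no cohort, and does not mention survival in that analysis. Its one criterion for further investigation is that "a CR/CRi/MLFS rate of at least 35% is achieved for frontline patients (Cohort B").

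Survival appears elsewhere. Section 7.4 defines overall survival from the first day of treatment and says that the primary analysis does not censor it at transplant. The last paragraph of Section 10 plans Kaplan-Meier estimates of the time-to-event endpoints, with no cohort and no 12-month time point.

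**The concern.** The Analysis Plan is where a reader looks for the analysis that answers each primary objective. Here it conflicts with Section 2.1 in three ways.

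- The primary efficacy analysis is a response rate for the combination as a whole, whereas response is the primary endpoint of Cohort B only.
- Cohort A's primary endpoint is not part of that analysis.
- The success rule pairs a cohort letter with the other cohort's label.

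Someone following the text could report response as primary in both cohorts, or could apply the 35% response rule to the newly diagnosed patients, whose primary endpoint is survival. The conclusion about the regimen would then rest on response alone. The analyst would also have to assemble Cohort A's primary analysis from other sections, and could do so after seeing the data of an open-label, single-arm trial.

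**Working it through.** **1. The texts side by side**

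| Item | Cohort A | Cohort B |
|---|---|---|
| Label (Section 3.1) | frontline | relapsed/refractory |
| Primary endpoint (Section 2.1) | 1-year OS | CR/CRi/MLFS |
| Rates in the design (Section 10) | 59% historical, 65% target | 35% target |
| Prior (Section 10) | Beta(1.18, 0.82) | Beta(0.7, 1.3) |
| Primary efficacy analysis (Analysis Plan) | 1-year OS not included | CR/CRi/MLFS, with no cohort limit |
| Success rule (Analysis Plan) | none | at least 35%, population called frontline |

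In the success rule the cohort letter, the endpoint and the 35% all point to Cohort B. Only the population word points to Cohort A, so that word is the error.

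**2. Does the error reach the design?** The posterior after x successes in 20 is Beta(a + x, b + 20 − x).

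- Cohort A: x = 0.59 × 20 = 11.8, giving Beta(12.98, 9.02). The 95% interval is 0.383 to 0.781; the plan states (0.38, 0.78).
- Cohort B: x = 0.35 × 20 = 7, giving Beta(7.7, 14.3). The 95% interval is 0.170 to 0.556; the plan states (0.17, 0.56).

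The boundaries in Tables 1 and 3 follow from the stated priors and cut-offs, and all 40 stopping probabilities in Tables 2 and 4 reproduce to four decimals. The calculations use survival for A and response for B throughout. The contradiction is confined to the Analysis Plan's wording.

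**3. What is left open for Cohort A?** The document suggests two estimators: the beta-binomial posterior (design text) and Kaplan-Meier (last paragraph of Section 10). Suppose all 20 patients have known status at 12 months. The posterior mean is (1.18 + x)/22. The Kaplan-Meier estimate is x/20, with variance S(1 − S)/20 and a log-log interval.

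| Alive at 12 months | Posterior mean (95% CrI) | Kaplan-Meier (95% CI) | P(rate > 59%) | P(rate > 65%) |
|---|---|---|---|---|
| 12 | 0.599 (0.392–0.789) | 0.60 (0.357–0.776) | 0.546 | 0.322 |
| 13 | 0.645 (0.439–0.825) | 0.65 (0.403–0.815) | 0.713 | 0.496 |
| 14 | 0.690 (0.487–0.860) | 0.70 (0.451–0.853) | 0.845 | 0.674 |

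The point estimates differ by at most 0.01, and every interval contains both 59% and 65%.

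**4. Losses before month 12.** As an illustration, take 12 alive, 6 dead and 2 lost early. Counting the lost as dead gives a posterior mean of 13.18/22 = 0.60. Excluding them gives 13.18/20 = 0.66. The rule for losses therefore shifts the estimate more than the choice of estimator does under complete follow-up.

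**5. Choice of benchmark.** Suppose Cohort A were read as the plan reads Cohort B, by observed rate against a threshold (an assumption). Then 59% needs 12 of 20 (0.59 × 20 = 11.8) and 65% needs 13 of 20. The two readings differ only at exactly 12. In a single look at n = 20, that outcome has probability 0.5594 − 0.3804 = 0.18 if the true rate is 59%, and 0.7624 − 0.6010 = 0.16 if it is 65%.

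**The case against.** The best defence is that Cohort A's analysis can be read from the rest of the document. The design text gives its endpoint, historical rate, target, prior and sample size, and a credible interval that applies if the cohort runs to its end. Cohort B has a matching sentence, and the Analysis Plan carries that approach through to B's final analysis, so the natural reading for A is the same. Section 7.4 also presupposes a primary analysis of survival.

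Much of this stands. A reader might infer that Cohort A has no planned analysis at all; the documents do not support that. Two further inferences also fail:

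- One could argue that survival is excluded because it is missing from the sentence "Other efficacy endpoints (e.g. CR rate, CR/CRi rate, minimal residual disease negativity, or proportion of patients proceeding to HSCT) will also be estimated". That list is introduced as examples and excludes nothing.
- One could see a conflict in Section 2.2, which lists "relapse-free survival, event-free survival, and overall survival" as secondary. The survival distribution is a different quantity from the 1-year rate, and overall survival is properly secondary for Cohort B.

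The defence does not remove the contradiction. The sentence that defines the primary efficacy analysis still names response alone, for the combination without a cohort, and the success rule still misnames its population. Correct reading elsewhere does not make that text right.

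**Conclusion.** The point holds as an internal contradiction in the primary analysis and the decision rule. Taken literally, the Analysis Plan gives 20 of 40 patients a primary endpoint that Section 2.1 does not give them, and it puts the wrong population word in its only success rule.

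Its size is limited. Sample size, priors, stopping boundaries and operating characteristics are unaffected. With complete 12-month follow-up, the two candidate estimators agree closely (0.645 against 0.65 at 13 of 20).

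A reader might go further and infer that leaving the benchmark open would decide Cohort A's result. The figures do not bear this out. Every interval computed contains both benchmarks, a simple threshold reading would differ at one outcome only (probability 0.16 to 0.18), and the plan already calls 59% historical and 65% the target. Nor is a final success bar for Cohort A required: its objective is to determine the rate.

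Severity: should be fixed. The figures assume known 12-month status for all 20 patients, except in the loss illustration; the threshold probabilities also ignore early stopping.

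**What to change.** Amend the Analysis Plan in Section 10.

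1. In the success rule, replace the word *frontline* with *relapsed/refractory*. State that the CR/CRi/MLFS primary analysis and the 35% rule apply to Cohort B only.
2. State that Cohort A's primary efficacy analysis is the 1-year overall survival rate, counted from the first day of treatment, with a 95% credible interval under the plan's own Beta(1.18, 0.82) prior. Run it once every patient's 12-month vital status is known or the patient is documented as lost. Say in advance how a patient lost before month 12 enters the proportion; that rule is the sponsor's choice. Give the 12-month Kaplan-Meier estimate as the supporting analysis, which handles losses by censoring.
3. Report the Cohort A result against the 65% target and the 59% historical rate already in Section 10. Whether to add a final success bar is the sponsor's choice and is not part of this fix.

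The cost is a few sentences, including the analysis timing and the rule for losses. No extra patients or visits are needed, because the survival calls in Section 6.5 already continue until death.
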